## 4.2 Exclusion Criteria

A patient who meets any of the following exclusion criteria is ineligible to participate in the study.

- 4.2.1 Known allergy to vitamin C
- 4.2.2 Inability to swallow oral medication
- 4.2.3 Known or suspected malabsorption condition or obstruction
- 4.2.4 G6PDH deficiency

- 4.2.5 Uncontrolled viral, fungal, or bacterial infection
- 4.2.6 Active meningeal or central nervous system disease
- 4.2.7 Alternative HCT including haplo-identical and umbilical cord transplants
- 4.2.8 Non-myeloablative conditioning defined as TBI < 2 cGy
- 4.2.9 Pregnancy or breastfeeding
- 4.2.10 Medical, psychological, or social condition that, in the opinion of the investigator, may increase the patient's risk or limit the patient's adherence with study requirements

# 5 STUDY ENTRY AND WITHDRAWAL PROCEDURES

## 5.1 Study Entry Procedures

5.1.1 Required Pre-Registration Screening Tests and Procedures

Refer to the study calendar in Section  $\underline{12}$  for the screening tests and procedures that are required prior to registration.

5.1.2 Study Enrollment

The following are needed for patient registration:

- Completed, signed, and dated eligibility checklist
- Signed and dated consent form

The patient's initial enrollment data (eg, demographics, consent, eligibility, on study) will be entered into the OnCore database before treatment begins.

## 5.2 Study Withdrawal

A patient will be removed from the study for any of the following reasons:

- Consent withdrawal for study treatment and study procedures
- If, in the opinion of the investigator, it is in the best interest of the patient to do so
- The study has been closed by the Sponsor-Investigator

The reason for withdrawal from the study and the date the patient was removed from the study must be documented in the source documents and OnCore database.

# 6 TREATMENT PLAN

## 6.1 Study Treatment

6.1.1 Safety Lead-In Cohort

For the initial safety lead-in cohort of 14 patients, vitamin C deficiency will be confirmed by a standard clinical pathology laboratory blood test before the first dose of parenteral vitamin C (see Sections 12 and 13.3). Safety lead-in patients with confirmed vitamin C levels of 0.5 mg/dL or less (20) may proceed on study treatment.

## 6.1.2 Planned Vitamin C Regimen

All study patients will receive the following vitamin C regimen:

- Parenteral vitamin C 50 mg/kg/day divided in 3 doses beginning on posttransplant Day +1 and continuing through Day +14; each dose (16.7 mg/kg) given in 50 mL of 5% dextrose and water over 30 minutes every 8 ± 3 hours
- After completion of the parenteral vitamin C doses, oral vitamin C 500 mg twice each day beginning on Day +15 and continuing until Day +180

The vitamin C regimen will continue as described above even if the vitamin C levels are found to be within normal range at the time of testing (refer to Section 6.3 for testing time points).

## 6.1.3 Missed Doses

Missed doses of IV vitamin C will not be made up (see Section 7.1).

Patients will be instructed to take a missed dose of oral vitamin C on the same day, as soon as they remember, and to not take more than 2 doses of vitamin C on the same day to make up for doses that were missed on the previous day.

6.1.4 Monitoring Patient Adherence (Oral Vitamin C Regimen)

Following hospital discharge, patients will be instructed to bring any unused supply of vitamin C to visits with their study team.

Patient reports of self-administration and review of unused medication will be used to assess the patient's compliance with the oral vitamin C regimen.

# 6.2 Standard HCT Management

Other than the vitamin C regimen (Section 6.1) and the collection of blood samples for the correlative studies (Section 11), all pre- and post-transplant assessments, examinations, procedures, and treatment required for patients undergoing HCT will be carried out according to the standard approach of the MCC-VCUHS CIT Program.

#### 6.3 Post-Treatment Evaluation

- All patients will undergo standard blood tests for vitamin C and CRP at baseline, on transplant day 0, and at post-transplant days +14, +30, and +100.
- All patients will undergo a standard urinalysis at baseline and weekly through 1 week following the last dose of IV vitamin C.
- All patients will have blood samples collected for thrombomodulin, TNF- $\alpha$ , and cfDNA assays at baseline, on transplant day 0, and at post-transplant days +14, +30, and +100.
- Relevant and disease-specific restaging studies will be performed per standard procedures of the MCC-VCUHS CIT Program following transplantation or earlier if clinically indicated.

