#### **11.3 Blood Samples for Correlative Studies**

Blood samples will be collected for the planned correlative studies at the following time points:

- Baseline (before beginning conditioning)
- Day 0
- Day +14
- Day +30
- Day +100

Approximately 4 mL will be collected in each of three tubes at each time point: one tube for vitamin C, one tube for CRP, and one tube to be processed and stored for TNF- $\alpha$ , TM, and cfDNA studies.

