## 13.1.4 Statistical Analysis

The primary and secondary outcomes will be compared between the study cohort and a historical cohort matched for age, donor type, and diagnosis. The NRM rate will be compared to the historical 35% rate (see Section 13.2 below) using a onesided exact binomial test. Time-to-event outcomes (time to engraftment, acute and chronic GVHD, and overall and relapse-free survival) will be graphically represented with a Kaplan-Meier step-function and will be assessed for associations with serum vitamin C levels and patient demographic measurements using a Cox Proportional Hazards model. Associations between blood levels of vitamin C and other exploratory endpoints will be estimated using Spearman rank correlation coefficients.

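### The Day +14 vitamin C level, the only one taken during IV dosing, has no draw time set relative to an infusion, so it is confounded by time since the last dose

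*Combined protocol and SAP*

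**What the plan says.** Section 6.1.2 sets the IV phase: "Parenteral vitamin C 50 mg/kg/day divided in 3 doses beginning on posttransplant Day +1 and continuing through Day +14", with "each dose (16.7 mg/kg) given in 50 mL of 5% dextrose and water over 30 minutes every 8 ± 3 hours". The oral phase follows: "oral vitamin C 500 mg twice each day beginning on Day +15 and continuing until Day +180".

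Section 6.3 sets "standard blood tests for vitamin C and CRP at baseline, on transplant day 0, and at post-transplant days +14, +30, and +100". Section 11.3 repeats the same five time points and adds: "Approximately 4 mL will be collected in each of three tubes at each time point". Table 5 marks the correlative samples by day only.

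Section 11.4 asks for the time of collection on tubes that are stored for later assay. Vitamin C and CRP tubes are labelled by the clinical laboratory's own practice, and Section 11.5.1 likewise defers to that laboratory for the assay. No section ties a draw to an infusion or asks for the time since the last dose.

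The first correlative aim in Section 1.5 is the effect of parenteral vitamin C on blood levels. Section 13.1.3 lists levels over time as an exploratory endpoint. Section 13.1.4 relates serum levels to time-to-event outcomes in a Cox model and adds: "Associations between blood levels of vitamin C and other exploratory endpoints will be estimated using Spearman rank correlation coefficients".

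**The concern.** Baseline and Day 0 come before any study vitamin C, and Days +30 and +100 fall in the oral phase. Day +14 alone can show what the IV regimen does to blood levels while it is running. A tube drawn just after an infusion and a tube drawn 11 hours after the last one both comply with the plan. The gap can be longer still, because Section 7.1 holds IV doses for raised creatinine and does not make them up.

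Two patients with the same exposure could then have very different Day +14 values. If draw time is unrelated to outcome, this is noise that pulls rank correlations and Cox coefficients toward zero, so a null result would be hard to read. It need not be pure noise: a gap caused by a held dose is linked to kidney function, which may itself be related to outcome. Nothing in Section 13.1.4 adjusts for time since dose, and the plan does not require the data that such an adjustment would need.

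**Working it through.** **Which samples fall in the IV phase.** Infusions run from Day +1 to Day +14 and samples fall on baseline, 0, +14, +30 and +100. The only overlap is Day +14.

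**Dose check.** 50 mg/kg/day ÷ 3 = 16.67 mg/kg, which agrees with the stated 16.7. The formula in Section 9.1.1 gives a molar mass of 176.12 g/mol, so D = 16.7 ÷ 176.12 × 1000 = 94.8 µmol/kg per dose.

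**Allowed interval.** 8 − 3 = 5 h to 8 + 3 = 11 h.

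**Model (assumed, not in the documents).** One compartment with first-order elimination, at steady state on 30-minute infusions every 8 h. Assumed half-life is 0.5-8 h and volume V is 0.2-1.0 L/kg. Background is 21.5 µmol/L, the untreated Day 14 mean in Section 1.2.1, added to the dose-related rise. With k = ln 2 ÷ half-life:

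- peak rise (end of infusion) = D ÷ (0.5 × V × k) × (1 − e^(−0.5k)) ÷ (1 − e^(−8k))
- rise t hours after the start of the infusion = peak rise × e^(−k(t − 0.5))

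Example with V = 0.4 and half-life 2 h: k = 0.3466. Peak rise = 94.8 ÷ (0.5 × 0.4 × 0.3466) × 0.1591 ÷ 0.9375 = 232. Rise at 8 h = 232 × e^(−2.599) = 17.3. Ratio of measured values = (232 + 21.5) ÷ (17.3 + 21.5) = 6.5.

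Results at V = 0.4 L/kg (µmol/L). The SD due to draw time takes draws as uniform over the stated window of an exact 8 h interval.

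| Half-life (h) | Peak rise | Rise at 8 h | Peak-to-trough ratio with background | SD, any time | SD, last hour before dose |
|---|---|---|---|---|---|
| 0.5 | 171 | 0.0 | 9.0 | 40 | 0.0 |
| 1 | 201 | 1.1 | 9.8 | 52 | 0.3 |
| 2 | 232 | 17.3 | 6.5 | 60 | 2.1 |
| 4 | 303 | 82.5 | 3.1 | 63 | 4.5 |
| 8 | 464 | 242.3 | 1.8 | 64 | 6.3 |

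**Range over all assumed volumes.**
- Highest ratio (V = 0.2, half-life 1 h): (402 + 21.5) ÷ (2.2 + 21.5) = 17.9.
- Lowest ratio (V = 1.0, half-life 8 h): (185.6 + 21.5) ÷ (96.9 + 21.5) = 1.7.
- SD due to draw time: 16-128 µmol/L for draws at any time, and 0-13 in the last hour before a dose.

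**Share of variance due to draw time.**
- Against the only between-patient SD in the documents (13.8, Section 1.2.1), the share runs from 16² ÷ (16² + 13.8²) = 57% to 128² ÷ (128² + 13.8²) = 99%. That SD comes from patients not on the infusions.
- If patients also differ in volume and clearance (assumed CV 30-50%, V = 0.4), simulation gives 47-85% at half-lives of 1-2 h and 7-41% at 4-8 h. At CV 80% it gives 2-47%.

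**What pre-dose timing leaves.** With V = 0.4 and half-life 2 h, the rise is about 49 µmol/L at 5 h, 17 at 8 h and 6 at 11 h. The dosing window therefore still matters, and actual times are needed.

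**The case against.** The strongest reply is that draw time need not be the main source of variation. That depends on half-life, volume, differences between patients and ward habits, none of which the documents give. Uniform draw times are a worst case, and a fixed ward routine would narrow them. This stands, although no routine is described and the ± 3 hour dosing window would still vary the gap.

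A reader might also infer that draw time moves the measured value up to 40-fold. At 0.2 L/kg after a single dose, the rise at 0.5 h against 11 h is 399 against 10 µmol/L with a 2 h half-life (about 40-fold) and 448 against 133 with a 6 h half-life (about 3-fold). That leaves out the background. With it, the ratios are 420.5 ÷ 31.5 = 13 and 469.5 ÷ 154.5 = 3.

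Nor is it shown that a high reading would commonly hide deficiency, taken as below 28 µmol/L in Section 1.2.1. In that same calculation the rise at 8 h with a 2 h half-life is 30, so a patient at the mean background still has about 51 µmol/L then, and 31.5 at 11 h. Faster elimination or a larger volume would be needed.

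Three further points stand. A comparison of the Day +14 level with the earlier VCU series is not planned: Section 13.1.4 compares only primary and secondary outcomes with a historical cohort. That section does not say which time points enter the Cox and Spearman analyses. And the gap is partly recoverable, since the stored tube from the same time point must carry a collection time, although nothing links that time to an infusion.

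**Conclusion.** The point holds as one of confounding. The only on-infusion level has no set relation to a dose, and the protocol requires neither the time since the last infusion nor a collection time on the vitamin C tube itself. Within one patient the value may differ by a factor of about 1.7 to 18 according to when the tube is drawn, under the assumed half-lives, volumes and background. It is tempting to say that the level mainly reflects draw time. The documents do not support that: draw time dominates if elimination is fast and patients are fairly alike, and may not otherwise.

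The effect is limited to the correlative aim in Section 1.5, the exploratory endpoint on levels, and any analysis in Section 13.1.4 that uses the Day +14 value. The NRM test, the sample size and the stopping rules do not use it, and Section 6.1.2 continues the regimen whatever the level. The change is worth making because it is cheap and this sample is the only one that can answer the aim during IV dosing.

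**What to change.** In Sections 6.3 and 11.3 and Table 5, define the Day +14 correlative draw as a pre-dose sample, taken immediately before a scheduled infusion that day. Record the end time of the previous infusion and the draw time on the eCRF.

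In Section 13.1.4, state which time points enter the vitamin C analyses. Make pre-dose values the main Day +14 analysis, and account for the actual time since the last infusion, for example as a covariate in the Cox model and through a partial rank correlation. Keep mistimed samples in a sensitivity analysis instead of discarding them, since the trial has only 55 patients.

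The cost is less flexible draw timing on one day and a few eCRF time fields. No extra tube or visit is needed, and treatment does not change.

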6.5.1 Evaluation of Adverse Events (AEs)

Patients will continue to be evaluated for AEs until 6 months post-transplant.

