# 7 DOSING DELAYS/DOSE MODIFICATIONS

## 7.1 Vitamin C

During days 1-14, IV vitamin C will be held in patients who develop a serum creatinine of >2.0 mg/dL and resumed once serum creatinine is  $\leq$  2.0 mg/dL. Missed doses will not be made up.

During days 15-180, if a patient has a serum creatinine level of > 2.0 mg/dL definitely, probably, or possibly related to vitamin C (Section 8.1.8), the patient will be instructed not to take their oral vitamin C until the serum creatinine level is  $\leq$  2.0 mg/dL. Missed doses will not be made up.

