## 8.4 Time Period and Grade of AE Capture

AEs  $\geq$  grade 3 regardless of expectedness or attribution will be recorded for study tabulation and analysis beginning on Day 0 and continuing until Day 180. Toxicity assessments will include a review of all toxicities experienced during each assessment period. The highest grade of each relevant toxicity during that period will be recorded.

Exception: Cytopenias and changes in electrolytes will **not** be recorded. Only clinical events and lab values reflecting renal function (eg, creatinine, urinalysis results) will be recorded as AEs.

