#### 9.1.6 Drug Interactions

Acidification of the urine by ascorbic acid may cause precipitation of cysteine, urate or oxalate stones (renal calculi) and will alter the excretion of certain other drugs administered concurrently.

Large doses interfere with the anticoagulant effect of warfarin.

Ascorbic acid has on occasion been used as a specific antidote for symptoms resulting from interaction between ethanol and disulfiram (Antabuse®). It may be expected that the concurrent administration of high doses of vitamin C could interfere with the effectiveness of disulfiram given to patients to encourage abstention from alcohol.

Because ascorbic acid is a strong reducing agent, it interferes with numerous laboratory tests based on oxidation-reduction reactions. Diabetics taking more than 500 mg of ascorbic acid daily may obtain false readings of their urinary glucose test. No exogenous ascorbic acid should be ingested for 48 to 72 hours before aminedependent stool occult blood tests are conducted because false negative results may occur.

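### AE capture ends on the last planned dosing day with no post-dose window, and a vitamin C hold or renal stone below grade 3 need leave no AE record

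*Combined protocol and SAP*

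**What the plan says.** **Dosing.** Section 6.1.2 gives IV vitamin C on Days +1 to +14, then "oral vitamin C 500 mg twice each day beginning on Day +15 and continuing until Day +180".

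**AE capture.** Under Section 8.4, AEs of grade 3 or higher "regardless of expectedness or attribution will be recorded for study tabulation and analysis beginning on Day 0 and continuing until Day 180". Cytopenias and electrolyte changes are left out; clinical events and renal laboratory values are kept. Section 6.5.1 words the end differently: "Patients will continue to be evaluated for AEs until 6 months post-transplant". Section 8.3 separately requires every SAE to be recorded, and Section 8.1.3 defines these by seriousness, not grade.

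**Visits.** Table 5 marks toxicity assessments on Days 14, 30, 60, 100, 120 and 180. Footnote C gives the Day 180 visit a window of two weeks either way. Days 270 and 365 carry a physical exam and a GVHD assessment but no toxicity assessment.

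**Renal provisions.** Sections 9.1.6 and 9.1.7 name renal calculi as a risk of vitamin C. Section 7.1 holds the drug when creatinine exceeds 2.0 mg/dL. In the oral phase the rise must also be "definitely, probably, or possibly related to vitamin C (Section" 8.1.8). Section 6.3 adds: "All patients will undergo a standard urinalysis at baseline and weekly through 1 week following the last dose of IV vitamin C". Blood chemistries, which include creatinine, follow the transplant program's standard frequency throughout. Footnote G limits laboratory values on the eCRF to those that bear on endpoints or stopping criteria or that support a clinical AE.

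**The concern.** Objective 2.2.3 is to characterize the safety and tolerability of the whole regimen, of which the oral phase is by far the longest part. Two features of the data capture work against it.

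First, recording stops on the day dosing stops. A non-serious event that appears shortly after the last tablet lies outside the capture period, and the last scheduled assessment may come before the final two weeks of dosing.

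Second, the plan acts on a renal signal that it does not require anyone to record. Whether to hold oral vitamin C depends on an investigator's attribution of a creatinine rise. AE capture depends on a different threshold, grade 3, and nothing links the two. A patient could have the drug held for a rise judged related to vitamin C, and the AE tables could show nothing. A non-serious stone below grade 3 is in the same position, although it is a risk that the protocol itself names.

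There is no control arm, so the report's statement on renal tolerability will rest on how complete these records are.

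**Working it through.** **Inputs**

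- IV phase Days 1 to 14; oral phase Days 15 to 180 (6.1.2).
- AE recording Day 0 to Day 180 (8.4), or to six months, about Day 180 to 183 (6.5.1).
- Day 180 visit window ±14 days (Table 5, footnote C).
- Urinalysis to one week after the last IV dose (6.3); Table 5 marks Days 7, 14 and 21.

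**Step 1. The plan's own schedule.** Last urinalysis = 14 + 7 = Day 21, as marked in Table 5. Section 6.3 and the table agree.

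**Step 2. Post-dose window.** End of recording minus last planned dose = 180 − 180 = 0 days. If six months is read as Day 183, it is 183 − 180 = 3 days. If the oral phase is read as ending on Day 179, then under 8.4 it is 180 − 179 = 1 day. On each of these readings there is at most a few days of off-drug capture for a patient who completes treatment.

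**Step 3. Last scheduled assessment.**

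- Earliest: 180 − 14 = Day 166. Latest: 180 + 14 = Day 194.
- Oral dosing days: 180 − 15 + 1 = 166.
- Dosing days after an assessment on Day 166: 180 − 166 = 14.
- Share of the oral phase: 14 / 166 = 8.4%. Share of all 180 dosing days: 14 / 180 = 7.8%.
- If dosing ends on Day 179: 13 / 165 = 7.9%.

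These days remain inside the stated recording period. What is missing is a scheduled assessment after them.

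**Step 4. Which renal events must be recorded?**

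| Event | Required AE record? | Source |
|---|---|---|
| Serious renal event, any grade | Yes | 8.1.3, 8.3 |
| Renal event or renal laboratory value, grade ≥3, Day 0 to 180 | Yes | 8.4 |
| Grade 4 renal toxicity | Yes; also counts toward the stopping rule and is an event of special interest | 8.3, 8.4, 13.3 |
| Creatinine above 2.0 mg/dL with a hold, non-serious, below grade 3 | No | 7.1, 8.4, footnote G |
| Renal calculus, non-serious, below grade 3 | No | 8.4, 9.1.6, 9.1.7 |

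The Table 5 study drug reviews and the adherence checks in 6.1.4 may show that tablets were not taken. Nothing there asks for the creatinine value or its attribution.

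**Step 5. The grading assumption.** Section 8.1.6 adopts CTCAE v5.0, and the documents do not reproduce its thresholds. At one end, every creatinine above 2.0 mg/dL is grade 3 or higher, every hold up to Day 180 generates an AE, and only the stone gap could remain. At the other end, every hold is below grade 3 and none needs a record unless serious. The documents give no expected number of holds or stones, so the loss cannot be put as a count of patients.

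**The case against.** The case on the other side is substantial, and most of it stands.

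- A reader might infer that renal surveillance ends at Day 21. The documents do not support that. Creatinine continues at the program's standard frequency, the oral hold rule operates on Days 15 to 180, five toxicity assessments follow Day 21, and grade 4 renal toxicity is a stopping event. One test stops.
- A reader might infer that AE capture ends before treatment does. It ends with treatment. The visit window is symmetric, and an early visit does not shorten the recording period.
- It is tempting to add up grams and say that most of the vitamin C is taken after the last urinalysis. That compares unlike things. The daily dose is higher in the IV phase, and the documents give no basis for equating IV and oral grams as renal exposure. The limit on urinalysis is consistent between Section 6.3 and Table 5, and the revision history shows that it was added in the same version that clarified the stone risk. It reads as a deliberate choice.
- SAEs are recorded at any grade, and Section 8.3 sets no end date for them. A stone that leads to hospitalization is captured, possibly after Day 180 too.
- Section 13.1.2 defines the safety endpoint as related AEs of grade 3 or higher, and Section 8.4 collects what that endpoint needs. Renal insufficiency and hematuria are also listed in Section 8.5.2 as common after transplant, so milder findings are hard to attribute without a control arm.

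The last point limits the value of collecting more, but it does not close the gap. Section 7.1 already requires the investigator to judge attribution before holding oral drug. Recording that judgment adds no new assessment, and descriptive reporting leaves the endpoint unchanged.

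**Conclusion.** The point holds as a limited gap in safety capture and is a cheap improvement. For a patient who completes treatment, the post-dose AE window is 0 days under Section 8.4 and about 3 at most if Section 6.5.1 is read generously. Up to 14 of 166 oral dosing days (8%) may have no later scheduled toxicity assessment. Non-serious holds and stones below grade 3 need leave no AE record or attribution.

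This rests on planned dosing to Day 180 and, for the recording gap, on the assumption that CTCAE v5.0 places some of these events below grade 3. The number of events affected is unknown.

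The documents do not support the wider reading that renal risk goes unwatched for most of the regimen, and the urinalysis schedule is not an error. The primary endpoint, type I error and power are unaffected.

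**What to change.** **1. Close the end-of-treatment gap (Sections 8.4 and 6.5.1, Table 5).** Require the final toxicity assessment to cover events through the last vitamin C dose, whatever the visit date. Extend AE recording to Day 180 or a short fixed period after the last dose, whichever is later, and use the same wording in both sections. Thirty days is one example; it is a convention and does not come from the documents. With a last dose on Day 180 it would close on 180 + 30 = Day 210. The earliest Day 270 visit is 270 − 14 = Day 256, so that visit can read out the whole window.

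**2. Record the named renal events (Section 8.4).** Record renal calculi, and each creatinine value that triggers a Section 7.1 hold, at any grade with its attribution. Report them descriptively beside the grade ≥3 endpoint of Section 13.1.2, which stays as it is.

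**Cost.** An amendment, a few more AE entries, and a toxicity mark at a visit that already exists. Some of the added entries will be transplant-related and hard to attribute. A readout at Day 270 comes 46 to 74 days after Day 210 (256 − 210 and 284 − 210), so it relies on chart review and recall. For patients already treated, creatinine values from routine care can be taken from source records, but attribution would be retrospective.

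No extension of urinalysis and no change to any dose or hold rule is proposed.
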